### ***Outcomes***

The primary endpoint of this study was to assess, and compare, the difference in the incidence of early breast cancer between two groups using different breast cancer screening methods (AI-assisted ultrasound screening/routine ultrasound screening). Early cancers should meet any of the following criteria at the time of diagnosis: less than 20 millimeters in diameter, no metastatic lymph nodes in the axilla, no distant metastasis, non-invasive cancers, stage 0, stage I, and stage IIA IIB (T2N1M0) breast cancer according to AJCC 8th staging.

The secondary aim was to determine the sensitivity, specificity, positive predictive value, and negative predictive value of the screening methods (AI-assisted ultrasound screening/routine ultrasound screening). Screening-detected cancers were defined as breast cancers positive for screening tests. We defined interval cancers as: breast cancers diagnosed after a negative screening test; breast cancers diagnosed after an indeterminate screening

test, but without any follow-up mammography or diagnostic examinations. A true-positive screening result was a positive result in a participant who was diagnosed with breast cancer by further diagnostic work-up. A false-positive screening result was a positive result in the absence of breast cancer. A true-negative screening result was a negative result in the absence of breast cancer and a false-negative test result was a negative result followed by diagnosis of interval cancer.

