### ***Randomization method***

Randomization was conducted by cluster, where districts rather than individuals were chosen as units of randomization. In order to avoid transfer between control and intervention cluster, urban levels were used as our strata. We then randomly selected one district out of seven urban areas as intervention cluster and another one out of nine suburban areas as control cluster.

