Participants receiving final negative results were exempt from additional diagnostic procedures. By contrast, those receiving final positive results were referred to Fudan University Shanghai Cancer Center for further diagnostic work-up to exclude or diagnose breast cancer. To assess interval cancers, we obtained data from all diagnosed breast cancers, plus an additional one year of follow-up from the Shanghai municipal cancer registry, one of the largest cancer registries globally, and an associate member of the International Association of Cancer Registries (IARC). For participants diagnosed with breast cancer outside of screening (ie, diagnosed with interval cancer), we collected all medical records. Two experienced radiologists reviewed the screening MG and ultrasound images from the study and the clinical MG and ultrasound images used for diagnosis of breast cancer, and reached a consensus on whether or not the breast cancer could retrospectively be identified in the screening.

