#### ***Sample size calculation***

Sample size was primarily calculated by expected detection and incidence data from breast cancer. According to the positive detection rate of Asian women with suspicious breast cancer lesion (5/1000), 16,000 participants were required. Based on the reported data by Shanghai Center for Disease Control and Prevention in 2017, the age-specific incidence rate of breast cancer among women aged 35-69 in urban Shanghai was 125.75/100,000, so that 20 breast cancer cases were expected to be screened. Our previous breast cancer screening study showed that the early stage rate of screen-detected breast cancer reached 83%, predicting about 17 breast cancer at early stage would be diagnosed in this study. All this would meet the evaluation needs of endpoint indicators.

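### Early-cancer incidence as the only primary measure cannot separate earlier detection from higher background incidence or extra in-situ diagnoses, and no planned outcome shows the difference

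*Combined protocol and SAP*

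**What the plan says.** All references are to the combined protocol and SAP.

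- **Outcomes.** The primary endpoint is "to assess, and compare, the difference in the incidence of early breast cancer between two groups using different breast cancer screening methods". On the definition: "Early cancers should meet any of the following criteria at the time of diagnosis". The list includes absence of distant metastasis as one entry and ends with "non-invasive cancers, stage 0, stage I, and stage IIA IIB (T2N1M0) breast cancer according to AJCC 8th staging". On the rest: "The secondary aim was to determine the sensitivity, specificity, positive predictive value, and negative predictive value of the screening methods". No outcome counts cancers outside the early definition, the early share, or the stage distribution.
- **Randomization method.** The arms are "one district out of seven urban areas as intervention cluster and another one out of nine suburban areas as control cluster".
- **Sample size calculation.** The plan expects 20 cancers among 16,000 women, from an urban Shanghai rate of 125.75 per 100,000. It then applies an earlier screening study in which "the early stage rate of screen-detected breast cancer reached 83" percent, and projects about 17 early cancers. No suburban rate and no in-situ share are given.
- **Screening procedure.** For interval cancers, "we obtained data from all diagnosed breast cancers", with a further year from the municipal cancer registry.
- **Statistical analysis.** Incidences are compared by Poisson regression. No adjustment for background incidence is stated.

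**The concern.** Early-cancer incidence rises when a screening method moves diagnoses from late to early stage. It also rises when the district simply has more breast cancer, and when more non-invasive lesions are labelled that would not have progressed. The endpoint gives the same reading in all three cases.

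With many randomised clusters, background incidence would tend to balance. Here there is one district per arm, drawn from different strata, so an urban–suburban difference in incidence is inseparable from the difference in screening method.

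The accuracy measures do not fill the gap. Sensitivity could have offered a check less dependent on incidence, but the Statistical analysis section divides true positives by true plus false positives, which is the positive predictive value.

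The definition makes matters worse. If meeting any one criterion suffices, absence of distant metastasis alone makes a cancer early, and the endpoint comes close to total non-metastatic incidence.

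At stake is what a positive result may be said to mean.

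**Working it through.** **Inputs.** N = 16,000, incidence 125.75 per 100,000 and early share 83% (Sample size calculation). Assumed here: 8,000 per arm, because the split is not stated, and the 83% applied to all cancers, although the plan gives it for screen-detected cancers in an earlier study.

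**Step 1. The plan's own figures.** 16,000 × 125.75/100,000 = 20.12 cancers (stated 20). 20.12 × 0.83 = 16.7 early (stated about 17). Both reproduce. The remainder is 20.12 × 0.17 = 3.4 late.

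**Step 2. Per arm, no difference of any kind.** 8,000 × 125.75/100,000 = 10.06 cancers. Early: 10.06 × 0.83 = 8.35. Late: 10.06 × 0.17 = 1.71.

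**Step 3. Two ways to raise the endpoint without a stage shift.** Both sizes are illustrative.

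| Scenario in AI arm | Early, AI vs control | Ratio | Late, AI vs control | Early share, AI vs control |
|---|---|---|---|---|
| Background incidence 30% higher | 8.35 × 1.3 = 10.85 vs 8.35 | 1.30 | 1.71 × 1.3 = 2.22 vs 1.71 | 83% vs 83% |
| Four extra in-situ lesions | 8.35 + 4 = 12.35 vs 8.35 | 1.48 | 1.71 vs 1.71 | 12.35/14.06 = 87.8% vs 83.0% |

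The first row leaves the early share unchanged but raises late cancers. The second raises the early share and leaves late cancers unchanged. No single added figure detects both. The early share among invasive cancers alone is unmoved in the second row, because the extra lesions are not invasive; it is also unmoved in the first if stage mix is the same in both districts.

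**Step 4. For comparison, a pure stage shift.** If the number of cancers per arm stayed at 10.06 and every late cancer became early, the ratio would be 10.06/8.35 = 1.20. A larger ratio needs more cancers in total, which is why total incidence must be shown beside early incidence.

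**Step 5. Chance of a significant result favouring AI with no stage shift.** Simulated Poisson counts, two-sided 5% level, Wald or likelihood-ratio test:

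| Background ratio, AI to control | Chance |
|---|---|
| 1 | 2–3% |
| 1.25 | 6–8% |
| 1.3 | 7–9% |
| 1.5 | 13–15% |
| 2 | 37–40% |

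If cancers were instead found at 5 per 1,000 in the control arm (the plan's positive detection rate, used here as an upper case), the chances at ratios 1.25, 1.5 and 2 would be 15–16%, 44–45% and 92%.

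**The case against.** Several points on the other side have force.

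- **The endpoint claims only a difference in early-cancer incidence.** This is correct: the Outcomes section does not promise a stage shift, and the 83% serves only to project a count, so it does not contradict the endpoint. The concern is with how a positive result would be read.
- **The scenarios are invented.** The 30% and the four lesions are illustrations. If the suburban district had the higher incidence, the bias would run against AI. A reader might infer that the plan favours the AI arm; the documents do not support that. Nor is a false positive likely at modest differences: at 30% it is 7–9%.
- **The late counts are uncertain.** The earlier study's definition of early is not given. Under the literal any-one-criterion wording, the late group could be nearly empty.
- **The root cause is the allocation.** A stage table does not repair one district against one district. The early share is protected from background differences only if the two districts have the same stage mix, which is not shown.
- **A simple decision rule would not work.** It is tempting to accept earlier detection if early incidence is higher and late incidence is not, or if the early share is higher. Four extra in-situ lesions satisfy both limbs in expectation (Step 3). Under a 30% background excess and identical screening, about 59% of simulated trials with more early cancers in the AI arm pass one limb or the other. With about two late cases per arm, such a rule would lend false reassurance.

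These points limit the size of the claim and the form of the remedy. They do not give the plan an outcome that separates the three explanations.

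**Conclusion.** The concern holds as a limit on interpretation. Taken alone, the primary endpoint cannot distinguish earlier detection from higher background incidence or additional in-situ diagnoses, and the urban-versus-suburban allocation makes any background difference coincide with the screening contrast.

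The documents do not establish the direction or size of any bias. The ratios of 1.30 and 1.48 rest on 8,000 women per arm, an 83% early share of all cancers, and the two illustrative scenarios. The structural point needs none of these.

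A reader might also infer that adding a late-stage outcome would let the trial prove or disprove a stage shift. It would not: about 3.4 late cancers are expected in total, which supports description and not a test.

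**What to change.** 1. **Reconcile the definition of early** in Outcomes, so that absence of distant metastasis alone does not qualify a cancer. The stage-based outcomes below depend on this.
2. **Add to Outcomes, by arm, with 95% CIs and over the same follow-up window:** (a) total cancer incidence and non-early incidence by AJCC stage; (b) the early share among all cancers and among invasive cancers only; (c) early invasive and non-invasive incidence separately.
3. **State the permitted wording in Statistical analysis.** A higher early-cancer incidence alone is reported as a difference in early-cancer incidence. The terms stage shift and earlier detection are used only if the early share among invasive cancers is higher and late-stage incidence is lower, each shown with its CI.

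**Cost.** SAP wording and one table. The cancers are already collected, and classifying them as early already requires staging. The late-stage comparison will be imprecise and the conclusion more cautious. Participants and intervention dates the database seal to January 2024, so outcomes added after that must be labelled post hoc. None of this removes the confounding of district with screening method, which the report should state as a limitation.

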### ***Participants and intervention***

Two women and children's care centers from randomly selected two districts were the main study locations. Women in the intervention arm received AI-assisted ultrasound conducted by trained female primary health workers, while women in the control arm received routine ultrasound conducted by doctors from the Maternal and Child Health Hospital. Participants in both arms were eligible for further diagnostic evaluation and treatment at Fudan university Shanghai cancer center and women in both groups were offered access to obtain rapid treatment at the hospital. Recruitment was started in January 2021 and completed in December 2022. All participants were then followed up till the end of 2023. The database was sealed in January 2024 for analysis.

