#### ***Statistical analysis***

Numerical data were shown as means and standard deviation (SD) and categorical variables in percentages. Sensitivity was determined via dividing the numbers of true-positive screening by the numbers of true-positive and false-positive screening. Specificity was determined via dividing the numbers of true-negative screening by the numbers of true-negative and false-negative screening. To calculate 95% CIs, we did bootstrapping based on 5000 samples. The significance of the differences of incidences was assessed using Poisson regression. For categorical variables we used Fisher's exact test or likelihood-based  $\chi^2$  test.

All analyses were done with IBM SPSS (version 20).

This study was performed according to the guidelines of the Helsinki Declaration and was approved by the Medical Ethics Committee of Fudan University Shanghai Cancer Center (No. 2008223-22). Informed consent was obtained from all individual participants included in the study.

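### Read literally, the either-or definition of early breast cancer in the primary endpoint makes every non-metastatic cancer early and voids the stage limit in the same sentence

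*Combined protocol and SAP*

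**What the plan says.** The Outcomes section of the combined protocol and SAP sets the primary aim: "The primary endpoint of this study was to assess, and compare, the difference in the incidence of early breast cancer between two groups". It then gives the combining rule for the case definition: "Early cancers should meet any of the following criteria at the time of diagnosis". The list opens with a diameter under 20 mm and continues: "no metastatic lymph nodes in the axilla, no distant metastasis, non-invasive cancers, stage 0, stage I, and stage IIA IIB (T2N1M0) breast cancer", by AJCC 8th staging. The items are separated by commas. None is made conditional on another.

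The Statistical analysis section applies the definition to the comparison: "The significance of the differences of incidences was assessed using Poisson regression". The Sample size calculation section plans on a prior-study figure, "the early stage rate of screen-detected breast cancer reached 83" per cent, "predicting about 17 breast cancer at early stage would be diagnosed in this study". It does not say which definition of early stage that figure used. The Participants and intervention section reports: "The database was sealed in January 2024 for analysis".

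**The concern.** With an either-or rule, meeting one item is enough. Absence of distant metastasis stands as its own item, so it admits every M0 tumour, including those beyond the stages named at the end of the sentence. The wording then measures something close to all breast cancer, while the stage items suggest that a restricted, early-stage event was meant.

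This matters because it is the event counted in the primary comparison. Suppose screening shifts an M0 cancer from beyond the T2N1M0 limit to within it. A stage-based count rises by 1, and the literal count does not change. The two rules therefore answer different questions about the intervention.

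The plan is dated 2020/08/17 but describes the database sealing of January 2024 in the past tense, so it does not show when this wording was settled relative to the data. Nothing suggests that a reading was chosen after results were seen. The present text would allow it, and that opening should be closed.

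**Working it through.** **Step 1: apply each rule to the possible cases.** Invasive tumours are sorted by size, nodes and metastasis, all taken from the sentence in Outcomes.

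| Cancer at diagnosis | Literal either-or rule | Listed stages only |
|---|---|---|
| M0, within the listed stages | early | early |
| M0, beyond the listed stages | early (metastasis item) | not early |
| M1, under 20 mm | early (size item) | not early |
| M1, node-negative | early (node item) | not early |
| M1, 20 mm or more, node-positive | not early | not early |

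Under the literal rule only the last row is excluded. T2N1M0 is itself M0, so it already qualifies through the metastasis item and the bracketed limit does no work. Requiring all the items together is no way out: it contradicts the stated connective, and T2N1M0 is node-positive, so it would fail the node item.

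**Step 2: reproduce the plan's figures** (Sample size calculation).

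- Expected cancers: 16,000 × 125.75/100,000 = 20.12 (plan: 20).
- Expected early cancers: 20.12 × 0.83 = 16.70 (plan: about 17).
- Not early: 20.12 − 16.70 = 3.42, which is 17% of 20.12.

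**Step 3: size the gap between the rules.** The documents give no stage distribution, so the result is conditional.

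*If the 83% reflects the listed stages.* Let s be the share of the 3.42 that is at once 20 mm or more, node-positive and M1. The literal early count is 20.12 − 3.42s.

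| s (assumed) | Literal early count | Added to 16.70 |
|---|---|---|
| 0 | 20.12 | 3.42 (20.5%) |
| 0.25 | 19.26 | 2.57 (15.4%) |
| 0.50 | 18.41 | 1.71 (10.2%) |
| 0.75 | 17.55 | 0.86 (5.1%) |
| 1 | 16.70 | 0 |

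*If the 83% reflects the literal rule.* All 3.42 remaining cancers would have to be 20 mm or more, node-positive and metastatic. The stage-based count would be at most 16.70, and the documents do not say how far below. That so large a share of screen-detected cancers would have all three features hints that a stage-based definition was meant. It is not proof, because the 83% is undefined.

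**Step 4: what this can do to a comparison (assumed numbers).** Let each arm have 10 cancers, all M0, with 9 within the listed stages in one arm and 7 in the other. The stage rule gives a difference of 9 − 7 = 2; the literal rule gives 10 − 10 = 0.

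The stage-based cases are a subset of the literal cases, so no significance test between the two counts is offered.

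**The case against.** The strongest reply is that this is loose drafting that any clinician would read correctly. The list overlaps elsewhere (non-invasive cancers beside stage 0), an item covered by a broader one is redundant rather than contradictory, and size, nodes and metastasis may have been meant as a single description. That may well be the intention, but the sentence states a combining rule and the grouped reading departs from it. A grouped reading and a stage-only reading are both plausible, and the text selects neither. Even the stage-only reading is incomplete, because the IIA/IIB item has no conjunction and it is unclear what the bracket qualifies.

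A second reply is that no effect on the between-arm difference has been shown: the range concerns pooled planning counts and includes zero. That is correct and stands. So does the remark that the two cases in the sizing are not exhaustive. If the prior study used a definition narrower than the listed stages, the stage-based count would lie between 16.70 and 20.12 and the gap would shrink.

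Third, Outcomes does not say that interval cancers enter the primary endpoint, so a wording fix should not decide that. This is fair, and the change below asks only that one rule be used for whichever cancers are counted.

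**Conclusion.** The concern holds: the definition is wrong as written. Followed literally, it makes every M0 cancer early, admits some M1 cancers, and leaves the T2N1M0 item without effect. No other section repairs it or shows which rule was used to code cases.

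The size is conditional. If the 83% reflects the listed stages, the literal rule adds between 0 and 3.42 events to a planned 16.70; where in that range depends on a stage distribution that the documents do not give. No direction of bias between arms can be derived. It is a must-fix because this is the case definition of the primary endpoint, and that grading does not rest on the size of the effect.

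**What to change.** - Replace the either-or list with one rule based on the AJCC 8th stages already named: stage 0, I, IIA and IIB at diagnosis. The sponsor should confirm what the T2N1M0 bracket qualifies.
- If the size, node and metastasis items are kept, require all three jointly, as an alternative to a listed stage.
- Apply the rule identically in both arms and, so far as each is counted, to screen-detected and interval cancers.
- State which definition lies behind the 83%.
- Date the clarification. Say which definition was used to code cases and whether arm-level results had been seen.
- Report a sensitivity analysis under the literal wording, so that readers can see whether the choice matters.

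The cost is a dated clarification and one extra analysis. If cases were coded by stage, no event changes. If they were coded literally, recoding is needed and the count may fall, by 0 to about 3.4 events on the planning figures if the 83% reflects the listed stages. Staging review looks feasible for interval cancers, since Screening procedure states: "For participants diagnosed with breast cancer outside of screening (ie, diagnosed with interval cancer), we collected all medical records". The plan does not state that T, N and M were recorded for screen-detected cases. The reference to AJCC staging at diagnosis makes it likely, but the sponsor should confirm it.

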**NCT number: 20210712**

**Date: 2020/08/17**

## **Study Protocol and Statistical Analysis Plan**

### ***Study population***

The program of “Two Cancer (breast and cervical cancer) Screening” has been launched in China since 2009 to provide free screening tests for millions of rural women aged 35-59 years (Ministry of Health of China and All-China Women’s Federation). This program has been expanded to all eligible women in both rural and urban areas as a basic public health service since 2019. Based on this program, we conducted a prospective cluster randomized controlled screening trial in Shanghai, China.

Eligible women were aged 35–70 years without a history of breast cancer, including in-situ cancer or other cancers in the previous five years, without serious cardiopulmonary insufficiency, liver or kidney insufficiency or other systemic diseases, and with life expectancy of more than five years.

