### ***Screening procedure***

Our screening procedure is based on the national Breast Cancer Screening Process Technical Guidelines issued in 2015 by the National Health Commission of People's Republic of China as follows:

(1) Clinical examination and initial breast ultrasound screening: all the participants were enrolled and received clinical examination and initial breast ultrasound or AI-assisted ultrasound. The initial screening test results were classified based on BI-RADS; (2) MG re-screening: participants with BI-RADS grade 0 or 3 were then suggested to receive MG. MG results were classified based on BI-RADS; (3) Histopathological examination (hereinafter referred to as biopsy): participants with BI-RADS grade 4 to 5 either in initial ultrasound test or MG test were suggested for further biopsy examination. For patients with MG rescreening of grade 0 or grade 3, short-term follow-up (three to six months) or further biopsy examination were suggested according to experts' evaluation; (4) Follow-up: participants with BI-RADS level 1 to 2 either in ultrasound or MG were under strict follow-up through visits and phone calls by trained medical social workers.

Final screening results (positive or negative) were based on a two-step approach. Initial screening results were determined by breast ultrasound and defined as negative with BI-RADS grade 1 or 2, positive with BI-RADS grade

4 or 5, and indeterminate with BI-RADS grade 0 or 3. Participants with indeterminate initial results were informed of the suspicious lesion detection and referred to MG assessment. The result in this second step was classified as negative or positive according to MG BI-RADS grade.

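### Interval cancers, and hence false negatives, have no fixed time window after the index screen, so their number depends on when each woman enrolled

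*Combined protocol and SAP*

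**What the plan says.** - **Outcomes.** Interval cancers are "breast cancers diagnosed after a negative screening test", together with cancers that follow an indeterminate test when neither mammography nor a diagnostic work-up was done. A false negative is a negative result followed by an interval cancer. A true negative is a negative result with no breast cancer. None of these carries a time limit. The sentence before them reads "Screening-detected cancers were defined as breast cancers positive for screening tests".
- **Screening procedure.** Each woman has one initial test ("all the participants were enrolled and received clinical examination and initial breast ultrasound or AI-assisted ultrasound"), with mammography if the result is indeterminate. To find interval cancers, "we obtained data from all diagnosed breast cancers, plus an additional one year of follow-up from the Shanghai municipal cancer registry". The start of that year is not given. The section also says "For participants diagnosed with breast cancer outside of screening (ie, diagnosed with interval cancer), we collected all medical records", and has two radiologists review the images to judge whether the cancer could have been seen at screening.
- **Participants and intervention.** "Recruitment was started in January 2021 and completed in December 2022", and "All participants were then followed up till the end of 2023".
- **Statistical analysis.** Sensitivity is written as TP/(TP+FP) and specificity as TN/(TN+FN).

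**The concern.** A false negative should be a cancer that was present at the index screen and was missed. Without a window, a tumour that first arises 30 months after a correct negative result is scored in the same way. The longer a woman is observed, the more such cancers accumulate, so the false-negative count reflects length of follow-up as well as the quality of the screen.

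Length of follow-up is set by enrolment date, because everyone is followed to the same calendar date. Each arm is a single district, and neither the Randomization method nor the Participants and intervention section balances enrolment dates between the two. If one district recruited earlier, its screening method would be charged with more false negatives at the same true accuracy. The comparison of sensitivity and NPV, which is the secondary aim, would then partly measure recruitment timing. With about 20 cancers expected in all, a handful of reclassified cases changes the sensitivity estimate visibly.

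**Working it through.** **Inputs from the plan.** 16,000 women; incidence 125.75 per 100,000; 20 cancers and about 17 early cancers expected; positive detection rate 5/1000 (all from Sample size calculation). Recruitment from January 2021 to December 2022 and follow-up to the end of 2023 (Participants and intervention).

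**Assumptions.** The incidence is annual (the plan gives no time unit). Recruitment is even over the 24 months. There are 20 true positives, and 4 cancers are missed and surface within 12 months. The plan gives none of these. The incidence is for urban Shanghai, whereas one cluster is suburban, so half the rate is also shown.

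**1. The plan's own figures.** 16,000 × 125.75/100,000 = 20.12, stated as 20. 20 × 0.83 = 16.6, stated as about 17. Both reproduce.

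**2. Time at risk.** A woman enrolled in January 2021 is followed for about 36 months, and one enrolled in December 2022 for about 12. With even recruitment the mean is about 24 months, of which 12 lie beyond the first year.

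**3. Background cancers if all 16,000 women were observed for the stated time.**
- 12 months: 20.12 × 1 = 20.1
- 24 months: 20.12 × 2 = 40.2
- 36 months: 20.12 × 3 = 60.4

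The pool from which late false negatives can come therefore varies threefold between the first and the last woman enrolled.

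**4. Effect on sensitivity, using TP/(TP+FN).** Beyond the first year there are on average 16,000 × 1 = 16,000 woman-years, giving 16,000 × 0.0012575 = 20.1 later cancers, or about 10.1 at half the rate.
- 12-month window: 20/(20+4) = 83%
- 10 later cancers added: 20/(20+4+10) = 20/34 = 59%
- 20 later cancers added: 20/(20+4+20) = 20/44 = 45%

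The match between this 83% and the plan's 83% early-stage share is a coincidence.

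**5. A second illustration.** Keep 20 true positives, and let between 10% and 50% of background cancers surface after a negative screen (assumed).
- 12 months: 20/(20+2.0) = 0.91 to 20/(20+10.1) = 0.67
- 24 months: 20/(20+4.0) = 0.83 to 20/(20+20.1) = 0.50
- 36 months: 20/(20+6.0) = 0.77 to 20/(20+30.2) = 0.40

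**6. Effect on NPV, TN/(TN+FN).** At 5/1000 there are 80 positives, leaving about 15,920 negatives. With 4 false negatives the NPV is 1 − 4/15,920 = 99.97%. With 24 it is 1 − 24/15,920 = 99.85%. The shift is about 0.1 percentage point.

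**The case against.** Four arguments stand against the point.

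**The plan does mention a year.** If the additional registry year runs from each woman's screen, it comes close to a 12-month window and most of the effect disappears. But it can equally be read as the year from the end of recruitment to the end of 2023, which agrees with the Participants and intervention section. The Outcomes definitions refer to neither reading, so the mention does not settle the matter.

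**The radiologists' review separates missed from new cancers.** It does so descriptively. Nothing in Outcomes uses the result to decide what counts as a false negative.

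**The sensitivity figures are not what the written formula would give.** This is correct. As printed, sensitivity does not contain false negatives at all; they enter only the quantity labelled specificity, which has the form of an NPV. The formula is a separate error, and the window matters for sensitivity only once that error is repaired.

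**The definition serves a secondary aim.** This also stands, and it limits the severity.

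Some stronger readings are tempting but not supported:

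- A reader might infer that Outcomes contradicts Screening procedure, since only the latter limits interval cancers to those found outside screening, and that cancers found at a later round would be scored as misses. The public programme does continue ("This program has been expanded to all eligible women in both rural and urban areas as a basic public health service since 2019"), but the plan describes one screen per woman and no later round. With one screen, the two wordings pick out essentially the same cases.
- A reader might infer that a cancer counts however late it is diagnosed. Follow-up ends with 2023, so the period is uneven but bounded.
- A reader might infer that the comparison between arms is already biased. The plan gives one shared recruitment period and no enrolment dates by arm. A difference is possible, not shown.

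**Conclusion.** The point holds as a gap in the definition. Interval cancers have no fixed window from the index screen, the registry year has no stated start, and women are at risk for anything from about 36 to 12 months. Cancers arising well after a true-negative screen are therefore counted as missed, and how many depends on enrolment date.

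The sensitivity figures show that the choice of window can dominate the estimate. They do not predict the trial's result, because they rest on assumed counts, even recruitment and an annual reading of the incidence. NPV is barely affected in absolute terms. The primary endpoint, incidence of early breast cancer, does not use this definition. Should-fix.

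**What to change.** Use one definition in both Screening procedure and Outcomes:

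- Count as interval cancers, and hence as false negatives, only breast cancers diagnosed within 12 months of each woman's index screen.
- Keep the two categories that Outcomes already has: after a negative result, and after an indeterminate result with no work-up. Widening this to every result that was not positive would sweep in women whose cancer was caught by the planned work-up.
- Apply the same 12-month window to true negatives.
- List cancers diagnosed after 12 months separately, by arm.
- Do not reclassify a woman as disease-free because a cancer found within 12 months came to light at a later screen. That would hide genuine misses.
- State when the additional registry year begins.

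The cost is small: new wording, and use of the screening and diagnosis dates. Detection route is not needed. Twelve months is feasible because even the last woman enrolled has about that much follow-up. The downside is that slow-growing misses that surface after 12 months leave the main estimate, although they remain visible in the separate list.
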